## Chapter 1: Overview

### 1.1. Executive Summary

Antibiotic use has saved many lives, but also comes with the issue of selecting for antibiotic-resistant organisms.

In this study, we hope to determine the effect of antibiotic use post-surgery on bacterial resistance and gain a better understanding of how antibiotic use during the perioperative period influences local and systemic antibiotic resistance in the individual.

### 1.2. Objectives

1: Determine if the use of topical ocular antibiotics for eye surgeries will lead to local (ocular surface) antibiotic resistance. *We hypothesize that topical ocular antibiotics for eye surgeries leads to ocular surface antibiotic resistance.*

2: Determine if the use of topical ocular antibiotics for eye surgeries will lead to systemic antibiotic resistance. *We hypothesize that topical ocular antibiotic use for eye surgeries leads to systemic antibiotic resistance.*

3: Determine if the frequency of topical ocular antibiotic usage for eye surgeries affects local antibiotic resistance. *We hypothesize greater frequency of topical ocular antibiotic usage for eye surgeries will increase local antibiotic resistance.*

### 1.3. Study Partners

This study was designed by investigators at UCSF. Funding is supported by internal grants.

### 1.4. Study Site

The study visits will be conducted at Mount Zion and Mission Bay campus at UCSF.

The study samples will be stored and processed at the Heintz Lab at [name].

## **Chapter 2: Context**

**Antibiotic use has saved millions of lives globally. However, this comes at the cost of selecting for antibiotic-resistant organisms at the individual and community level.** It is estimated that every year, approximately 700,000 deaths are associated with drug resistance globally. This places a significant burden on the public health system and the judicious use of antibiotics is more important than ever before.

**There exists little consensus on the use of antibiotics in ophthalmology, whether it's frequency, type of antibiotics, or when to use antibiotics.** In the US, when or how the patients are instructed to take antibiotics for eye procedures is generally dependent on the individual ophthalmologist, which leads to a wide range of practice patterns. Furthermore, there are almost no randomized controlled trials evaluating the effects of commonly used topical antibiotics on antibiotic resistance at the local or systemic level in the host.

**The proposed masked, randomized controlled trial evaluates the effects of topical antibiotic use on the selection for antibiotic resistance genes at the local and systemic levels.** The results will provide guidance for antibiotic usage in ophthalmology and have the potential to inform public health policies.

## **Chapter 3: Study Design**

The research team will assess antibiotic resistance over four weeks, comparing frequency of antibiotic use among adult patients undergoing ocular surgeries. All eligible participants will be randomized. A random sample of 108 (36/arm) participants from UCSF will be selected to participate in the "ARIES" study, which will entail biospecimen collection via nasopharyngeal, conjunctival, buccal, and rectal swabs 1-week post-op. Baseline will entail conjunctival swab collection. 4-week post-op sample collection will include conjunctival, nasopharyngeal, and buccal swabs. All biologic specimens collected will be stored and made available to [name] for laboratory testing of antibiotic resistance.

[figure not shown]
### **3.1. Randomization**

**Randomization of Treatment Allocation.** All eligible UCSF adult patients undergoing ocular surgery will be randomized in a 1:1:1 fashion to three groups:

- **Group 1:** intraoperative/intracameral antibiotic (moxifloxacin) only; no postoperative antibiotic drops
- **Group 2:** intraoperative/intracameral antibiotic (moxifloxacin); postoperative antibiotic drops four times a day for 1 week and then stop
- **Group 3:** intraoperative/intracameral antibiotic (moxifloxacin); postoperative antibiotic drops once a day for 1 week and then stop

Refer to SAP for randomization details.

**Study Participants:** UCSF adult patients undergoing ocular surgeries will be recruited if they consent and the study doctor deems the participant meets all study criteria.

**Figure 1: Trial Profile**

## **Chapter 4: Study Eligibility**

### **4.1. Eligible Participants**

To be eligible for the trial, participants must meet the following criteria:

1. Over 18 years of age
2. Undergoing cataract surgeries that would benefit from intracameral antibiotics
3. Able to provide swabs
4. No systemic antibiotics within the past 3 months or within one month after the cataract surgery
5. No immunosuppression medications such as Prednisone, Methotrexate, Cellcept, or anti-TNF inhibitors within the past 3 months
6. No patients needing tubes or trabs
7. No allergy to fluoroquinolones
8. Has ability to consent for the study

#### 4.2. Study Schedule

The schedule for examination and treatment is shown below in Table 1:

	Pre-Op	1-Day Post-Op	1-Week Post-Op	4-Week Post-Op
Consent	X			
Randomization	X			
Specimen Collection	X		X	X
Survey		X	X	X

## **Chapter 5: Core Study Elements**

An overview of core elements for the ARIES study is provided here but will be described in more detail in the following chapters.

We will conduct the following study activities for the ARIES study:

### **Recruitment**

UCSF adult patients undergoing cataract surgeries will be recruited if they meet the criteria as written above.

### **Enrollment**

The study will be explained by the study doctors or study coordinators. The patient will be enrolled in the study after obtaining written consent from the patient (and witness if needed).

The participant will be randomly assigned to one of three groups only after obtaining consent.

### **Survey**

An ocular symptom/quality of life survey (DEQ-5 and SPEED questionnaires) will be given to the patient to be filled at 1-Day post-op, 1-Week post-op, and 4-Week post-op.

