## **Chapter 9: Sample Organization, Transport, and Storage**

### **9.1 De-identification**

All specimens will be labeled in the outpatient clinic with a random identification number linked to their name, MR number, and surgical/ocular disease history, but to facilitate masking, only the designated Study Coordinator and the Biostatistician will have access to the key linking the ID with patient information. Age, gender, and surgical/ocular disease history will be available for each specimen, but names will be kept confidential. Therefore, all specimens will be de-identified. Please note that the Study Coordinator who is unmasked to the study arms will not be collecting samples at 1-week post-op (primary end point) to prevent potential biases.

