### **9.4 Catalog Specimens**

We will create a list of study data and specimens, including the age, gender, surgical history, ocular disease history, group participant was in, and symptom questionnaire. We will also list the date of collection and transport, and the storage conditions while in the field and while banked at UCSF. This will facilitate identification of specimens for future analyses.

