#### **10.6.2 Active Adverse Events Monitoring**

### **Ocular Symptoms/Quality Survey**

To identify any adverse events during the study, the research team will administer the survey (DEQ-5 and SPEED questionnaires) to each participant at 1-day, 1-week, and 4-weeks after surgery. This survey will be completed by the participants themselves before specimen collection.

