#### **Open and Closed Reports**

For each DSMC meeting, Open and Closed Reports will be provided. Open Reports will include data on recruitment and baseline characteristics, pooled data on eligibility violations, and completeness of follow-up and compliance. The study statistician ([name]) will prepare these Open Reports.

Closed reports, available only to those attending the Closed Sessions of the meeting, will include analyses of primary and secondary efficacy endpoints, including subgroup and adjusted analyses, AEs and symptom severity, and Open Report analyses that are displayed by intervention group. These Closed Reports will be prepared by the study biostatistician.

The Open and Closed Reports should provide information that is accurate, with follow-up that is complete to within two months of the date of the DSMC meeting. The Reports should be provided to DSMC members approximately three days prior to the date of the meeting.

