## Appendix 3. DEQ-5 Questionnaire

**DEQ 5****1. Questions about EYE DISCOMFORT:**

a. During a typical day in the past month, how often did your eyes feel discomfort?

0  Never  
 1  Rarely  
 2  Sometimes  
 3  Frequently  
 4  Constantly

b. When your eyes felt discomfort, how intense was this feeling of discomfort at the end of the day, within two hours of going to bed?

Never have it      Not at all intense      Very intense  
 0       1       2       3       4       5

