**1. Report the type of SYMPTOMS you experience and when they occur:**

Symptoms	At this visit		Within past 72 hours		Within past 3 months	
	Yes	No	Yes	No	Yes	No
Dryness, Grittiness or Scratchiness						
Soreness or Irritation						
Burning or Watering						
Eye Fatigue						

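### The DEQ-5 and SPEED survey, the only active adverse-event tool listed, has no pre-operative score; adding one is a cheap, optional improvement

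*Protocol*

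**What the plan says.** The Survey section of Chapter 5, in both documents, states that the DEQ-5 and SPEED survey "will be given to the patient to be filled at 1-Day post-op, 1-Week post-op, and 4-Week post-op". Section 4.2 introduces the visit table ("The schedule for examination and treatment is shown below in Table 1"). There the Pre-Op column is marked for consent, randomisation and specimen collection but not for the survey, which is marked only at the three post-op visits. Section 10.6.2 repeats the three post-op times.

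The same section gives the purpose of the survey: "To identify any adverse events during the study". It lists no other active tool; section 10.6.1 adds passive reporting by patients. Under Open and Closed Reports (13.5), the closed DSMC reports include "AEs and symptom severity". The survey is the likely source of the severity data, although the text does not say so.

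Some pre-operative information is collected in other forms:

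- Section 9.1: "Age, gender, and surgical/ocular disease history will be available for each specimen".
- Section 9.4 catalogues "ocular disease history, group participant was in, and symptom questionnaire" together.
- DEQ-5 item 1a (Appendix 3) asks "During a typical day in the past month, how often did your eyes feel discomfort"; items 2a and 3 use the same one-month window.
- SPEED item 1 (Appendix 4) asks yes or no for three windows: the visit itself, "Within past 72 hours", and the past three months.
- The scored SPEED items, frequency and severity, state no recall window. The form in the Protocol totals them out of 28.

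**The concern.** Both questionnaires measure dryness, irritation, watering and similar complaints, which a patient may well have before cataract surgery. If the first score is taken the day after surgery, a high value may be a longstanding complaint or a new one, and the form alone cannot readily say which. That matters for a tool whose stated job is to detect adverse events. The available text gives no rule for calling a symptom new or worse.

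The second loss is statistical. A pre-op score is usually the best single predictor of a post-op score on the same scale. Without it, differences between patients that existed before surgery stay in the error term, and a chance imbalance between arms cannot be adjusted away.

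**Working it through.** **Inputs from the documents.** Chapter 3 gives 108 participants, 36 per arm; 3 × 36 = 108, which agrees. Section 3.1 gives 1:1:1 allocation. No alpha, power, SD, effect size or dropout is given for the survey in the available text, so there is no stated survey power figure to reproduce.

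**Assumptions.** Two-sided alpha 0.05, no multiplicity correction, 80% power, SD = 1, no dropout, and correlation r between pre-op and post-op score of 0.3, 0.5 or 0.7. The documents give no value for r.

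**Without a pre-op score.** The 95% CI half-width for a pairwise difference is t(0.975, 70) × √(2/36) = 0.470 SD. The difference detectable with 80% power is 0.670 SD from the two-sample t test. The normal approximation, (z(0.975) + z(0.80)) × √(2/36), gives 0.660 SD, which confirms the scale.

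**With a pre-op score as covariate.** Residual variance is multiplied by 1 − r². The CI half-width and the detectable difference are multiplied by √(1 − r²), and the equivalent sample size is 36/(1 − r²). The single degree of freedom spent on the covariate is ignored.

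| r | Variance remaining | Variance cut | Equivalent n per arm | CI half-width (SD) | Detectable difference (SD) |
|---|---|---|---|---|---|
| 0 | 1.00 | 0% | 36 | 0.470 | 0.670 |
| 0.3 | 0.91 | 9% | 39.6 | 0.448 | 0.639 |
| 0.5 | 0.75 | 25% | 48.0 | 0.407 | 0.580 |
| 0.7 | 0.51 | 49% | 70.6 | 0.336 | 0.478 |

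**Do the existing data replace a pre-op score?** Only in part.

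- Ocular disease history is not a symptom score.
- The three-month SPEED column is yes/no, lies outside the scored total, and also covers the days since surgery.
- The 1-day DEQ-5 frequency items look back over a window in which about 29 of 30 days precede surgery. If patients answer literally, they come close to a baseline. They are still answered after surgery and after allocation, and the intensity items 1b and 2b name no window of their own.

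**The case against.** The strongest reply is that little depends on this. None of the three objectives in section 1.2 concerns symptoms. The available text plans no hypothesis test on DEQ-5 or SPEED, so the detectable differences above describe an analysis not shown to be planned. Randomisation keeps the by-arm comparison free of systematic baseline bias, passive reporting also runs, and the correlation is assumed. All of that stands, and it is why the point is optional. It does not answer the difficulty in the individual patient, which remains whatever the correlation.

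Three stronger readings are tempting, and the documents support none of them.

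- **A reader might infer that the arm comparison is biased for lack of a baseline.** It is not: allocation is random, and what is lost is precision and the chance to adjust for accidental imbalance.
- **A reader might infer that the one-month DEQ-5 recall dilutes early arm differences by a calculable amount.** At 1 week about 23 of 30 days in the window precede surgery, but the form asks about a typical day and does not say how patients weigh the days. Only items 1a, 2a and 3 carry that window, worth 12 of the 22 DEQ-5 points. The SPEED total, collected at the same visits, is not tied to it. The two worries also pull against each other: literal recall makes the 1-day frequency items a near-baseline, while non-literal recall leaves little dilution.
- **A reader might infer that the SAP omits a suitable analysis.** The SAP is listed as Appendix 1, but its text was not available, so nothing can be said about what it omits.

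**Conclusion.** The point holds as a cheap, optional improvement. The survey schedule is the same throughout both documents and contains no pre-op score, although a pre-op contact already exists. The cost to the trial is a less precise symptom comparison and weaker attribution of symptoms in individual patients.

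The size of the precision loss rests on the assumed correlation and is nil if that is zero. The benefit for attribution does not rest on it. The by-arm comparison remains valid, and the resistance endpoints and objectives are not affected. The one-month recall of the DEQ-5 is a caution for interpretation only.

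**What to change.** In Table 1, the Chapter 5 Survey section and section 10.6.2, add DEQ-5 and SPEED at the Pre-Op contact, after consent and before randomisation. The order matters: Groups 2 and 3 take drops at home and Group 1 does not, so a score taken once the arm is known could be coloured by it. Unless the SAP already does so, add one sentence stating that post-op scores are analysed with adjustment for the pre-op score.

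Keep the DEQ-5 wording as it is, and read the 1-day and 1-week totals beside the SPEED total.

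The cost is a few minutes of questionnaire time per participant at a contact already held, and a line of analysis text. No visit or treatment changes. A pre-op score cannot be recovered after surgery, so patients already operated on gain nothing.

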### **Specimen Collection**

All participants will have NP swabs, conjunctival swabs, and buccal swabs collected by the study doctors or study coordinator. Rectal swabs will be collected by the patient themselves by following instruction guide (see Appendix).

All specimens will immediately be placed in a Zymo preservative after collection and labeled with the participants study number. Samples will then be transported to the Heintz laboratory at [name] for long-term storage at -80C and processing.

Conjunctival swabs will be collected prior to surgery. Conjunctival, NP, buccal, and rectal swabs will be collected 1-Week post-op. Conjunctival, NP, and buccal swabs will be collected 4-Week post-op.

### **Specimen Processing**

Metagenomics deep sequencing (MDS) and or directed PCRs will be conducted on all collected samples. Trained laboratory technicians in the Ralph & Sophie Heintz laboratory will be responsible for processing all samples.

## **Chapter 6: Registering Participants for Specimen Collection**

Samples will be collected with reference to age, surgical history, and history of ocular disease, but participant names will not be included in laboratory records to ensure privacy. Samples will thus not be associated with an individual's name, but with a random identification number, masking laboratory personnel and preventing identification of individuals.

At each time point, each participant selected for specimen collection will be assigned an identification number for database anonymity.

## **Chapter 7: Specimen Collection for Resistance and Microbiome Testing**

### **7.1 Participants**

We will collect nasopharyngeal, conjunctival, buccal, and rectal swab samples from all 108 participants. The swabbing will occur prior to surgery (conjunctival), 1-week post-op (conjunctival, NP, buccal, rectal), and 4-Week post-op (conjunctival, NP, buccal). The enrolled participants will be given instructions on when and where to go for swabbing visits after surgery.

### **7.2 Conjunctival, Nasopharyngeal, Buccal, and Rectal Swabs**

All swabs will be stored in DNA/RNA shield media by Zymo and MDS and/or directed PCRs will be performed on all samples to evaluate for changes in antibiotic resistance and microbiome.

#### **7.2.1 Conjunctival Swabs:**

The examiner will:

1. Have the patient sit or lay on a chair with their head well supported. The chair will be adjusted to the appropriate height to ensure the patient's safety.
2. Each individual will use new bottle of proparacaine eyedrop for local anesthesia before taking conjunctival sample. Instruct the patient to look up and expose the conjunctiva by gently pulling down the lower lid of the surgical eye. Gently sweep the conjunctival swab along the lower fornix from inner to outer canthus without touching the eyelids.
3. Place each swab in a separate tube containing 2.0 mL DNA/RNA shield media by Zymo, break it off at its natural break-off point, and close the cap of the tube with the swab immersed.
4. Place study number label on the collection tube and then store at -80C until processing.

#### **7.2.2 Nasopharyngeal Swabs:**

The examiner will:

1. Place an adult flocked swab with a nylon tip through the right nostril and down the nasopharynx of each participant. Note that if the swab is not perpendicular to the frontal plane of the face, it is likely not in the inferior turbinate.
2. Once you reach the nasopharynx, rotate the swab 180° as you remove the swab from the nose.
3. Place the swab in a tube containing 1.0 mL DNA/RNA shield media by Zymo media, cut the handle off using sterile scissors, and close the cap of the tube with the swab immersed.
4. Place study number label on the collection tube and then store at -80C until processing.

Do not attempt to collect the NP swab if you are not successful after **three** attempts.

#### **7.2.3 Buccal Swabs:**

The examiner will:

1. Have the patient rinse mouth with water prior to sample collection
2. Instruct the patient to open their mouth and insert the buccal swab into one side of their mouth, between the cheek and upper gum. Press firmly and twirl swab against the inside of their inner cheek and over the gums for at least 30 seconds using an up/down and front/back motion on each side (1 minute total for both sides). Hold the swab as close to its head as is comfortable for the patient. While you rub the cotton swab, turn the plastic shaft. This will ensure the entire tip is covered with cells from the cheek. This sampling technique should collect buccal cells without drawing blood.
3. Place the swab in a tube containing 2.0 mL DNA/RNA shield media by Zymo, break the swab at its break-off point, and close the cap of the tube with the swab immersed.
4. Place study number label on the collection tube and then store at -80C until processing.

#### **7.2.4 Rectal Swabs:**

The test will require that the participant themselves to obtain a good sample. It is important to describe the test to the participant thoroughly to ensure a good sample is taken. The rectal swabs include an instruction guide (see Appendix) with the following instructions:

1. Put on a clean pair of gloves.
2. Partially open the fecal swab package and remove the top section of the collection vial (this can be discarded).
3. Remove the swab from the package. Take care that the cotton tip is not touched. If it is touched, throw the swab away and begin with a new one.

4. Insert the tip of the swab into your anus only as far as needed to contact fecal material (1-3cm) and rotate 180 degrees. The tip should be a brownish color when removed.
5. Place swab into the preservative in the collection tube. Make sure the swab is fully submerged in the liquid preservative and then break the swab off using the pre-scored breaking point.
6. Screw the cap back on the tube and make sure that it's tightened. Wrap the area where the cap meets the tube with Parafilm to ensure that the sample will not leak, and then place the tube into the appropriate sample box.
7. If the swab cannot be broken off while the tip is fully submerged in the liquid, try twirling the swab in the liquid first (to release the contents of the sample into the preservative) before breaking it off. Avoid rubbing the sample on the tip of the swab off on the side of the tube where there is no liquid.
8. Hand the tube with the sample to the investigator/study coordinator.
9. The investigator/study coordinator places the number label on the collection tube.
10. Tube will be stored at -80C until sample processing.

### **7.2.5 Materials for Swab Collection for Molecular Testing**

#### **Swabs**

Conjunctival, NP, and buccal specimens will be collected using sterile, individually wrapped adult flocked swabs with a plastic swab shaft (manufactured by Copan or similar manufacturer). Rectal swab specimen will be collected using sterile individually wrapped swab (Zymo Research).

#### **Sample Tubes**

Conjunctival, NP, and buccal samples for molecular testing will be collected into sterile 2.0ml microcentrifuge tubes, manufactured by Sarstedt®. (DNA-free tubes will be used for collection in DNA/RNA shield (Zymo).) Rectal swab specimens will be stored in 2 mL sterile tube with DNA/RNA Shield solution provided as part of the DNA/RNA Shield Collection Tube with Swab (Cat # R1108).

